14.2 Exposure

All treated subjects were scheduled to receive two injections during Phase A of the trial and two injections during Phase B of the trial. A summary table of the number injections received will be provided. A list of lot numbers used in this study will be provided in the clinical study report.

15 CHANGES TO PLANNED ANALYSIS

For the Phase B exploratory biomarker endpoint, all changes were calculated from baseline instead of from Week 52.

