3.2.8 Phase B Exploratory Biomarker Endpoints

1. Change from Week 52 in serum bone biomarkers (e.g., P1NP and β -CTX) and a serum cartilage biomarker (e.g., COMP) through Week 104

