4.3 Treatment Blinding

Phase A of the study was double-blind. Study medication was provided to the investigational center, and the center identified unblinded personnel who were able to prepare and perform the injection of study medication and/or placebo. Study personnel administering or preparing study medication and reference therapy were to minimize any contact with the subject following the injection and not perform any study assessments throughout the duration of the study. Each site was required to document a blinding plan that identified the blinded and unblinded personnel at the investigational center and described how the study blind will be maintained.

Primary analysis of Phase A data was completed after the last subject completed Week 52 (EOSa). While the Sponsor was unblinded to study treatment after the Phase A analysis (after the last subject completed Week 52 [EOSa]), the Investigators and the subjects remained blinded for Phase B.

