8.1.1 Baseline

Baseline is defined as the last value recorded for any given parameter prior to first study medication injection on Day 1. For qCT and DXA, values recorded from Screening Visit 2 will serve as baseline, regardless of whether the scans took place before or after first study medication injection. Baseline values for Phase B of the study are the same as they were for Phase A.

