10 GENERAL SAFETY ANALYSIS

Whereas Phase A analysis (defined prior to unblinding) was the primary analysis for this study, data collected during Phase B complements the primary analysis by offering insight into safety after more than one year of treatment.

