13 EXPLORATORY BIOMARKER ANALYSIS

A statistical description of biomarkers COMP, P1NP, and β -CTX at baseline will be provided along with absolute and percent changes from baseline at each subsequent timepoint for subjects in the SAS.

Baseline-adjusted ANCOVA will also be used to analyze the change from baseline in these biomarkers and evaluated at Weeks 4, 12, 24, 36, 52 (EOSa), 64, 76, 88, and 104 (EOSb). Subject level listings will be provided.

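### The Phase B biomarker endpoint is defined as change from Week 52, but the SAP analyses only change from the Day 1 baseline and gives no reason

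*SAP*

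**What the plan says.** **Endpoint.** SAP 3.2.8 lists "Change from Week 52 in serum bone biomarkers" and a cartilage marker, through Week 104. Protocol 4.2.8 has the same wording. The markers named are P1NP, β-CTX and COMP. Unlike the Phase A biomarker endpoint (Protocol 4.2.4), the Phase B wording does not mention a comparison with placebo.

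**Analysis.** SAP 13 plans descriptive "absolute and percent changes from baseline at each subsequent timepoint for subjects in the SAS". It adds a model: "Baseline-adjusted ANCOVA will also be used to analyze the change from baseline in these biomarkers and evaluated at Weeks 4, 12, 24, 36, 52"; the sentence goes on to Weeks 64, 76, 88 and 104. SAP 8.1.1 fixes the reference: "Baseline values for Phase B of the study are the same as they were for Phase A". No summary or model of change from Week 52 is planned.

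**Disclosure.** SAP 15 states the change: "For the Phase B exploratory biomarker endpoint, all changes were calculated from baseline instead of from Week 52". It gives neither a reason nor a date.

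**Timing.** SAP 4.3 uses the past tense: "While the Sponsor was unblinded to study treatment after the Phase A analysis". SAP 10 opens "Whereas Phase A analysis (defined prior to unblinding) was the primary analysis for this study", and it makes that statement about the Phase A analysis only.

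**The concern.** The SAP lists one quantity and estimates another. The listed one isolates what happened during the second year; the estimated one accumulates everything since Day 1. For a marker that moved in Phase A and then stayed flat, the Week 104 contrast could be read as a second-year effect. For a marker that moved in Phase A and came back in Phase B, the Week 104 contrast would show nothing, although the change from Week 52 was real.

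The Week 52 reference looks deliberate. The Phase B BMD change endpoints (Protocol 4.2.6) and the efficacy change endpoints (Protocol 4.2.7) run from baseline, whereas the biomarker endpoint names Week 52, and change from baseline to Week 52 is already a Phase A endpoint. A change of reference written after sponsor unblinding, with no reason attached, leaves a reader unable to judge it.

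**Working it through.** **The plan's own figure.** No power or precision is stated for the biomarkers. The only design figure is 81.6% power for a BMD ratio (SAP 6). It reproduces: log-scale SD = √ln(1 + 0.30²) = 0.2936; distance = ln(0.93/0.80) = 0.1506; 50 per group, one-sided 0.05; the noncentral t gives 81.65%. It has no bearing on this point.

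**Step 1: the identity.** For one subject,

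(Week 104 − baseline) = (Week 52 − baseline) + (Week 104 − Week 52).

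Least squares is linear in the outcome. So, in the same subjects and with the same baseline covariate, the from-baseline ANCOVA estimate at Week 104 equals the Week 52 estimate plus the estimate for change from Week 52.

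**Step 2: size when a Phase A difference persists.** Assumptions, none of them in the documents: unit SD at each visit; equal correlation ρ between baseline, Week 52 and Week 104, from 0.5 to 0.8; n = 35 to 50 per arm; a between-arm difference D at Week 52, unchanged at Week 104; no dropout.

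- From-baseline contrast: mean D, SE = √[(2/n)(1 − ρ²)].
- Change from Week 52: mean 0, SE = √[(2/n) × 2(1 − ρ)].

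| n per arm | ρ | SE, from baseline | SE, from Week 52 |
|---|---|---|---|
| 35 | 0.5 | √(0.05714 × 0.75) = 0.207 | √(0.05714 × 1.0) = 0.239 |
| 50 | 0.8 | √(0.04 × 0.36) = 0.120 | √(0.04 × 0.40) = 0.126 |

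With D = 0.5, the ratio D/SE for the from-baseline contrast is 2.42 in the first row and 4.17 in the second. The normal approximation Φ(D/SE − 1.96) gives a nominal P < 0.05 in 68% and 99% of trials; simulation (2,000 runs per setting) gave 65% and 99%. With D = 0.3 the simulated range is 30% to 68%. Raw change from Week 52 averaged about 0 in every persistence setting, with nominal P < 0.05 in about 5%. These percentages only express size against noise, since no test is planned.

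**Step 3: size when a Phase A difference fades.** With D = 0.5 at Week 52 and 0 at Week 104, the from-baseline contrast averaged about 0 (nominal P < 0.05 in 4% to 5%), while change from Week 52 averaged about −0.50 SD.

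**Step 4: can a reader subtract?** The Week 52 contrast is tabulated beside the later ones, but on the SAS, which includes subjects who never entered Phase B. Therefore

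Week 104 (remaining subjects) − Week 52 (all sampled) = [Week 104 − Week 52, remaining subjects] + [Week 52, remaining − Week 52, all sampled].

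The second bracket is unknown from the tables. The SE is also unavailable, because it needs the covariance between visits. In the model of Step 2, treating the two estimates as independent inflates the SE by √(1 + ρ): 1.22 at ρ = 0.5 and 1.34 at ρ = 0.8.

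**Step 5: which covariate.** If change from Week 52 is adjusted for the Week 52 value, a persisting D contributes (1 − ρ)D with no new change: 0.5 × 0.5 = 0.25 SD at ρ = 0.5 and 0.2 × 0.5 = 0.10 SD at ρ = 0.8. Simulation gave about 0.25 and 0.10. Adjustment for the Day 1 value does not do this: it averaged about 0 in a check at the two table settings.

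**The case against.** **Change from baseline is defensible in itself.** It matches the other Phase B change endpoints, the fixed baseline in SAP 8.1.1 and the Phase A biomarker model, and it keeps a pre-randomisation reference. This stands, and is why that analysis should stay.

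**The trajectory is visible.** Contrasts at Weeks 52 and 104 appear together, and subject listings are planned. A flat or reversing course can be seen by eye. This largely stands. What is missing is an estimate of the listed quantity in one set of subjects, with its interval.

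**The endpoint is minor.** It is labelled exploratory, Protocol 10.2 rules out formal testing, and biomarkers are not among the safety parameters in Protocol 8.1. This stands, and limits the weight of the point.

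**The endpoint does not call for a between-arm contrast.** The wording omits placebo. Protocol 10.4.4 says Phase B follows Phase A, which supports a comparison, but within-arm change should be shown as well.

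**The protocol has a precedent for adjusting for the later reference value.** The Week 24 durability models in Protocol 10.4.3 do so. That precedent concerns other endpoints, and Step 5 shows the cost of following it here.

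**Stronger readings that the documents do not support.** A reader might infer that every Phase A difference reappears as a Phase B result; Step 3 shows that one which has faded does not. A reader might infer that the reported value is off by exactly the Week 52 difference; that holds only in the same subjects. A reader might also infer that unblinded results prompted the switch. Sponsor unblinding before Phase B ended was planned and disclosed (Protocol 4.1 and 10.6.1), a separate Phase B SAP was foreseen (Protocol 10.1), and nothing links the switch to any biomarker result.

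**Conclusion.** The point holds as a matter of interpretation and reporting. The Phase B biomarker endpoint listed in both documents is not estimated, and the SAP gives no reason for replacing it. The part of any Phase A difference that persists enters the Week 64 to 104 contrasts in full: about 0.50 SD against about 0 for the listed endpoint, if 0.5 SD persists unchanged. That size rests on assumed effect sizes, correlations and numbers per arm; the direction follows from the identity alone.

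That the SAP text follows unblinding rests on its own wording in Sections 4.3 and 10; I had no date page. This is not a type I error problem, and the documents give no evidence that the choice was driven by results.

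**What to change.** - **SAP 13:** for each marker, add change from Week 52 to Weeks 64, 76, 88 and 104 in subjects with both values. Show it within each arm and as the SM04690-minus-placebo difference with 95% CI, adjusted for the Day 1 baseline and not for the Week 52 value.
- **SAP 13:** keep the from-baseline ANCOVA, labelled as the cumulative effect since Day 1.
- **SAP 15:** say which of the two is the protocol endpoint, so that it agrees with SAP 3.2.8. Give the reason for the switch and its date relative to sponsor unblinding.

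The cost is SAP wording and a few more table lines per marker; the samples are already scheduled at Week 52 and at every later visit. The downside is slightly more output and a contrast limited to subjects with both samples.

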17 APPENDICES

17.1 Appendix 1 – Visit Windows

Visit	Monthly WOMAC and Patient Global Assessment	Pain NRS
Baseline	Last value before first injection	Day -7 to -1
Week 1		Day 1 to 7
Week 2		Day 8 to 14
Week 3		Day 15 to 21
Week 4	Day 26 to 32	Day 22 to 28
Week 5		Day 29 to 35
Week 6		Day 26 to 42
Week 7		Day 43 to 49
Week 8	Day 54 to 60	Day 50 to 56
Week 9		Day 57 to 63
Week 10		Day 64 to 70
Week 11		Day 71 to 77
Week 12	Day 82 to 88	Day 78 to 84
Week 13		Day 85 to 91
Week 14		Day 92 to 98
Week 15		Day 99 to 105
Week 16	Day 110 to 116	Day 106 to 112
Week 17		Day 113 to 119
Week 18		Day 120 to 126
Week 19		Day 127 to 133
Week 20	Day 138 to 144	Day 134 to 140
Week 21		Day 141 to 147
Week 22		Day 148 to 154
Week 23		Day 155 to 161
Week 24	Day 166 to 172*	Day 162 to 168
Week 25		Day 169 to 175
Week 26		Day 176 to 182
Week 27		Day 183 to 189
Week 28	Day 194 to 200	Day 190 to 196
Week 29		Day 197 to 203
Week 30		Day 204 to 210
Week 31		Day 211 to 217
Week 32	Day 222 to 228	Day 218 to 224
Week 33		Day 225 to 231
Week 34		Day 232 to 238
Week 35		Day 239 to 245
Week 36	Day 250 to 256	Day 246 to 252
Week 37		Day 253 to 259

Week 38		Day 260 to 266
Week 39		Day 267 to 273
Week 40	Day 278 to 284	Day 274 to 280
Week 41		Day 281 to 287
Week 42		Day 288 to 294
Week 43		Day 295 to 301
Week 44	Day 306 to 312	Day 302 to 308
Week 45		Day 309 to 315
Week 46		Day 316 to 322
Week 47		Day 323 to 329
Week 48	Day 334 to 340	Day 330 to 336
Week 49		Day 337 to 343
Week 50		Day 344 to 350
Week 51		Day 351 to 357
Week 52 (EOSa)	Day 362 to 368*	Day 358 to 364
Week 53		Day 365 to 371
Week 54		Day 372 to 378
Week 55		Day 379 to 385
Week 56	Day 390 to 396	Day 386 to 392
Week 57		Day 393 to 399
Week 58		Day 400 to 406
Week 59		Day 407 to 413
Week 60	Day 418 to 424	Day 414 to 420
Week 61		Day 421 to 427
Week 62		Day 428 to 434
Week 63		Day 435 to 441
Week 64	Day 446 to 452	Day 442 to 448
Week 65		Day 449 to 455
Week 66		Day 456 to 462
Week 67		Day 463 to 469
Week 68	Day 474 to 480	Day 470 to 476
Week 69		Day 477 to 483
Week 70		Day 484 to 490
Week 71		Day 491 to 497
Week 72	Day 502 to 508	Day 498 to 504
Week 73		Day 505 to 511
Week 74		Day 512 to 518
Week 75		Day 519 to 525
Week 76	Day 530 to 536*	Day 526 to 532
Week 77		Day 533 to 539
Week 78		Day 540 to 546
Week 79		Day 547 to 553
Week 80	Day 558 to 564	Day 554 to 560

Week 81		Day 561 to 567
Week 82		Day 568 to 574
Week 83		Day 575 to 581
Week 84	Day 586 to 592	Day 582 to 588
Week 85		Day 589 to 595
Week 86		Day 596 to 602
Week 87		Day 603 to 609
Week 88	Day 614 to 620	Day 610 to 616
Week 89		Day 617 to 623
Week 90		Day 624 to 630
Week 91		Day 631 to 637
Week 92	Day 642 to 648	Day 638 to 644
Week 93		Day 645 to 651
Week 94		Day 652 to 658
Week 95		Day 659 to 665
Week 96	Day 670 to 676	Day 666 to 672
Week 97		Day 673 to 679
Week 98		Day 680 to 686
Week 99		Day 687 to 693
Week 100	Day 698 to 704	Day 694 to 700
Week 101		Day 701 to 707
Week 102		Day 708 to 714
Week 103		Day 715 to 721
Week 104 (EOSb)	Day 726 to 732	Day 722 to 728

*Note: At Weeks 24, 52 (EOSa), and 76, the WOMAC and Patient Global Assessment must be completed prior to the Week 24, 52 (EOSa), and 76 study medication injections, respectively.

